#### Change history:

Version	Date	Major changes

CTU Bern	Statistical Analysis Plan ImaCorll	Date effective: 2		
	Based on CS_STA_TEM-11_SAPtemplate_v01			Page 3 I 16

b UNIVERSITÄT BERN

#### 2. Study synopsis

The summary of the protocol is only available in German, and will thus not be copied in the SAP.

*Hypothesis*: The study hypothesis is that hemodynamic monitoring using hTEE in critically ill patients with hemodynamic compromise allows for an expedited reversal of circulatory impairment compared to standard ICU monitoring.

*Primary Objective:* To assess the impact of hemodynamic monitoring using the ImaCor ClariTEE technology on time to reversal of shock in hemodynamically compromised patients in comparison to standard monitoring.

Secondary Objective: To assess the safety and tolerability of the ImaCor ClariTEE probe.

*Study design*: Open-label, randomized controlled, single-centre trial. Subjects will be randomized into four groups in a two by two factorial study design. Assessed factors are the method of monitoring (use of hTEE monitoring vs. conventional monitoring) and the frequency of monitoring (use of per-protocol intervals for hemodynamic assessment vs. standard assessment intervals).

**Primary outcomes:** Time to resolution of hemodynamic instability defined as systemic mean blood pressure (MAP) > 60mmHg for at least 4 hours after discontinuation of vasopressors or inotropes. The criterion is considered fulfilled if >90% of MAP measurements occurring every 1-2 minutes is > 60mmHg for a 4 hour period.

**Secondary outcomes**: Time to death. Time to resolution of clinical signs of hypoperfusion as a composite of capillary refilling time < three seconds, urine output > 0.5 mL/kg/h for at least 4 hours, and blood lactate < 2 mmol/L. Use of pulmonary artery catheter (yes/no), central venous catheter (yes/no), or conventional echocardiography (yes/no). Occurrence of adverse events assumed to be due to prolonged hemodynamic impairment and treatment with vasopressors/inotropes (as binary yes/no outcomes): cardiac arrhythmias, excessive vasoconstriction, and secondary infections.

Please see the protocol (Version 4.0, January 2018) for a detailed description of the study.

CTU Bern	Statistical Analysis Plan ImaCorll	Date effective:	2018-04-24
	Based on CS_STA_TEM-11_SAPtemplate_v01		Page 6 I 16

#### 3. Study objectives

#### 3.1. Primary objective

The primary objective of the study is to assess the impact of hemodynamic monitoring using the hTEE technology on time to reversal of circulatory shock in hemodynamically compromised patients in comparison to standard monitoring.

#### 3.2. Secondary objectives

Secondary objectives include the assessment of safety and tolerability of the hTEE probe.

#### 4. Study design

#### 4.1. General design

This is an open-label, randomized controlled, single-center trial. The study follows a two by two factorial design. Subjects are randomized into four groups: Use of hTEE monitoring vs. conventional monitoring, and use of per-protocol intervals for hemodynamic assessment vs. standard assessment intervals.

#### 4.2. Sample size

Sample size calculation is based on a retrospective analysis of a sample of 159 patients admitted to ICU of Inselspital Bern during a three-month period, which fulfilled the study entry criteria. Median time to resolution of hemodynamic instability as defined by discontinuation of vasopressors or inotropes in this sample was 18.5 hours. We used the Stata command artsurv to calculate the sample size (Barthel et al). We applied the unweighted logrank test and derived expected probabilities of hemodynamic stabilization and loss-to-follow up (i.e. death) over time from the retrospective analysis. To identify a clinically relevant reduction of time to resolution of hemodynamic instability of 25% (i.e. from 18.5 to 14.0 hours) we calculated a required sample size of 458 patients to achieve a power of 80% at a two-sided alpha level of 0.05 for the main effect (comparison of monitoring with/without hTEE). To account for an estimated drop-out rate of 10%, we choose a sample size of 125 patients for each of the four groups or 500 patients in total.

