#### 8.2. Definition of populations for analysis

#### 8.2.1. Full analysis set (FAS)

The full analysis set consists of all randomized patients fulfilling all inclusion criteria, regardless of whether they actually received the allocated monitoring or not or any subsequent protocol deviations during follow up visits. Patients will be analysed in the group they were randomized regardless of any cross-overs or loss to follow-up (intention-to-treat principle). This corresponds to the treatment-policy estimand.

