#### 9. Statistical analysis

#### 9.1. General

The primary analysis will be based on the FAS, analysing all patients in the treatment group they were randomized to. We will first test the primary hypothesis, the difference in time to hemodynamic stabilization between the hTEE and standard group. Second, we will evaluate the difference between the protocolled and standard monitoring. Differences in the primary outcome will be assessed using the Fine-Gray competing risk model accounting for the competing risk of death (Fine and Gray 1999).

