#### Primary analysis of primary endpoint

The analysis of the primary endpoint will be a superiority analysis based on the full analysis set, asking whether hTEE monitoring is superior in time to resolution of circulatory shock as compared to standard monitoring. We will use a Fine-Gray competing risk regression model accounting for the competing risk of death (Fine and Gray 1999), adjusted for the frequency of monitoring (protocolled vs standard).

The primary outcome will be censored after 6 days in the primary analysis, because continuous hTEE monitoring was only continued for 72h after randomisation. Patients which were discharged without reaching the primary endpoint before 6 days will be censored as well. The strength of the association between each covariate and the outcome is reflected by the sub-hazard ratio in these competing risks models. The sub-hazard ratio is the ratio of the hazard associated with the cumulative incidence function under different values of the covariate, taking into account the hazard of the competing event (death).

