#### Primary analysis of secondary endpoints

The secondary outcome time to death will be evaluated using Cox proportional-hazards regression. Other secondary time-to-event outcomes will be analysed using competing risk models as described above. Binary outcomes will be analysed using logistic regression, All models will be adjusted for the frequency of monitoring (protocolled vs standard).

CTU Bern	Statistical Analysis Plan ImaCorll	Date effective: 2018-04-24		
CTO Bern	Based on CS_STA_TEM-11_SAPtemplate_v01			Page 13 I 16

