### 9.5.2. Secondary comparison between protocolled vs standard monitoring frequency

Second, we will test the secondary hypothesis, the difference in time to resolution of circulatory shock between the protocolled and standard frequency monitoring group, adjusted for the method of monitoring.

We will analyse primary and secondary endpoints as described above. All models will be adjusted for the method of monitoring (hTEE vs standard).

We will also test for an interaction between the method (hTEE vs standard) and frequency of hemodynamic monitoring (protocolled vs standard) in order to assess if effects are different depending on the method and frequency of monitoring, entering an interaction term in the models described above.

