#### 9.6. Secondary analyses

Secondary analyses will include a per-protocol analysis as well as sensitivity analyses.

First, we will perform a per-protocol analysis based on the per-protocol analysis set.

Second, we will evaluate the primary endpoint censoring after 3 days and after 28 days using the FAS.

Finally, we will perform subgroup analysis for the method (hTEE vs. standard monitoring) and the frequency (per protocol vs. standard interval) of hemodynamic monitoring using the FAS.

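### The 80% power in SAP section 4.2 is for a logrank test that censors deaths; the primary test is Fine-Gray, so the figure applies to no planned analysis of the primary endpoint

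*SAP*

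**What the plan says.** Section 4.2 describes the calculation as follows: "We applied the unweighted logrank test and derived expected probabilities of hemodynamic stabilization and loss-to-follow up (i.e. death) over time". The probabilities came from a retrospective sample of 159 patients. The target is a fall in median time to resolution from 18.5 to 14.0 hours, and the section concludes that "we calculated a required sample size of 458 patients to achieve a power of 80% at a two-sided alpha level of 0.05" for the hTEE main effect. The total is then set at 500 to allow for 10% drop-out.

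The analysis sections name a different test. Section 9.1: "Differences in the primary outcome will be assessed using the Fine-Gray competing risk model accounting for the competing risk of death". Section 9.5.1, on the primary endpoint: "We will use a Fine-Gray competing risk regression model accounting for the competing risk of death", with the effect reported as a sub-hazard ratio, adjustment for monitoring frequency, and censoring at 6 days.

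Section 10 lists the competing risk model as a change from the protocol, made to account for death. It says nothing about power for that change, although it gives lack of power as the reason for another one, the ranking of the two factorial comparisons.

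**The concern.** The logrank test with deaths censored compares cause-specific rates of resolution among patients who are alive and unresolved. The Fine-Gray test compares sub-hazards, and patients who died stay in its risk set. The two tests answer different questions, and a given treatment effect generally gives them different effect sizes. If hTEE speeds resolution but leaves the death hazard unchanged, the sub-hazard ratio is usually closer to 1 than the rate ratio used for planning.

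What is at stake is interpretation. A non-significant primary result would be read as coming from a trial with 80% power, although nobody computed that figure for the test that produced the result. No p-value and no patient number changes.

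**Working it through.** **1. Reproducing 458.** Inputs from section 4.2: medians 18.5 and 14.0 h, two-sided alpha 0.05, power 80%, 1:1 on the hTEE margin. With exponential times the resolution rate ratio is 18.5/14.0 = 1.321, and ln 1.321 = 0.2787.

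Schoenfeld: events = 4(z₀.₉₇₅ + z₀.₈₀)² / (ln ratio)² = 4(1.960 + 0.842)² / 0.2787² = 31.40 / 0.0777 ≈ 404.

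404/458 = 88.2%, so 458 fits a logrank test in which about 11.8% of patients end without resolution. Power at 458 is Φ(√(404/4) × 0.2787 − 1.960) = Φ(0.841) = 80.0%. At 500 patients (441 events) it is Φ(0.967) = 83.3%. The figure is therefore plausible for the stated test. It cannot be confirmed exactly, because the SAP does not give the resolution and death probabilities that were used.

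**2. Looking for an analysis to which the 80% applies.**
- Section 9.5.1, primary endpoint: Fine-Gray.
- Section 9.5.1, secondary endpoints: "The secondary outcome time to death will be evaluated using Cox proportional-hazards regression". This is the only Cox model, and it is not for resolution. Other time-to-event endpoints use competing risk models.
- Section 9.5.2, frequency comparison: "We will analyse primary and secondary endpoints as described above", so the same models again.
- Section 9.6: a per-protocol analysis, subgroups, and "we will evaluate the primary endpoint censoring after 3 days and after 28 days using the FAS". The analysis set, the horizon or the subgroup changes; the model does not.

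None is a logrank or cause-specific analysis of time to resolution.

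**3. Why the effect size shifts.** Take constant hazards, 12% control-arm deaths and the same death hazard in both arms. The death hazard is then 0.12/0.88 = 0.136 times the control resolution hazard. The share dying unresolved under hTEE is 0.136/(1.321 + 0.136) = 9.4%. The ratio of cumulative sub-hazards at the plateau is ln(0.094)/ln(0.12) ≈ 1.12. The sub-hazard ratio starts near 1.32 and is pulled towards 1 as deaths accumulate in the risk set; a single fitted ratio lies in between.

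**4. Size, by simulation.** Assumptions not in the SAP: exponential resolution times with control median 18.5 h; 11.7% of patients dying unresolved, the share that fits step 1 (about 11% in the two rows with a lowered death hazard); no drop-out. Administrative censoring is at 144 h, as in section 9.5.1. There were 10,000 runs per scenario, with simulation standard error at most 0.5 points.

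| Assumption about death | Implied sub-hazard ratio | Fine-Gray power, 458 / 500 |
|---|---|---|
| Constant hazard, equal in both arms | 1.236 | 56% / 60% |
| Deaths only in first 24 h | 1.205 | 45% / 49% |
| Deaths only after 24 h | 1.291 | 74% / 77% |
| Deaths only after 48 h | 1.325 | 80% / 83% |
| Constant, hTEE lowers death hazard 10% | not computed | 66% / 70% |
| Constant, hTEE lowers death hazard 25% | not computed | 78% / 82% |
| 1.321 is itself the sub-hazard ratio | 1.321 (set) | 80% / 83% |

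Where 1.321 is the cause-specific ratio, logrank power is 79–80% at 458 and 83–84% at 500, in line with step 1. With no treatment effect, both tests reject in 5.0% of runs at 458.

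**5. Sensitivity.** With equal constant death hazards, moving deaths from 5% to 30% takes Fine-Gray power at 458 from about 67% to 46%. An exact 25% reduction (ratio 1.333) needs 380 events, or 380/458 = 83% resolving; with 16.5% deaths, Fine-Gray power is again about 56%. With 12% control-arm deaths and hTEE raising the death hazard by 20%, it is 41%.

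**The case against.** The strongest reply is that nothing is hidden. Section 4.2 names its test and its handling of death, section 10 declares the new model, and nowhere does the SAP claim 80% for Fine-Gray. The SAP was written before the final analysis, with randomization described in the past tense, so a new power figure cannot change the design. The result will be judged by the sub-hazard ratio and its confidence interval. The loss also rests on inputs that the SAP does not give: the death share, its timing, the effect of hTEE on death, and whether the 25% effect is meant as cause-specific. Several scenarios show no loss.

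Much of this stands, but it bears on the size of the loss, not on the mismatch. Disclosing the model change does not tell a reader that the 80% no longer refers to the primary test. Entering death as loss to follow-up favours the cause-specific reading of the effect, and section 4.2 never states a target sub-hazard ratio. Three further points are fair. The 500 column assumes no drop-out: 500 × 0.9 = 450 patients gives about 79% logrank power, so 458 is the better basis for comparison. A supportive cause-specific model is good practice, and its absence alone is not an error. The SAP does not say whether the retrospective data are still usable.

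**Conclusion.** The concern holds. On the text alone, the stated 80% belongs to no planned analysis of the primary endpoint. The 458 is not shown to be miscalculated for the logrank test, and the validity of the primary test is not in question.

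The size is illustrative. A shortfall is likely if the planned effect is cause-specific and hTEE leaves death roughly unchanged: about 56% instead of 80% at 458 patients with a constant death hazard, and 45% if deaths come early. It is about nil if deaths are late, if hTEE lowers the death hazard materially, or if 1.32 was meant as a sub-hazard ratio. Only the sponsor's retrospective data can narrow this range. The point should be fixed, but it concerns how the result is read.

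**What to change.** 1. In section 4.2, and in the row of section 10 on the competing risk model, state that the 80% power refers to the logrank (cause-specific) comparison with deaths censored, and not to the Fine-Gray primary test.
2. From the retrospective sample of 159 patients, not from trial data, recompute and state Fine-Gray power at the 6-day cut for 500 and for 458 patients. Say what is assumed about the effect of hTEE on death. The figures in this review should not be copied in. If the sample is no longer usable, say so and let step 1 stand alone.
3. In section 9.6, add a supportive cause-specific Cox or logrank analysis of time to resolution with deaths censored (FAS, 6-day cut, adjusted for monitoring frequency), reported next to the sub-hazard ratio.

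The cost is two sentences, one recomputation and one extra model, with no extra patients and no change to the primary test. The drawbacks are one more result to report and a stated power that will probably look less favourable.

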#### 4.3. Randomization

Subjects were randomized to a total of four groups by block randomization using sequentially numbered, identical, opaque, letter-sized, sealed envelopes, selecting a block size of four.

CTU Bern	Statistical Analysis Plan ImaCorll	Date effective: 2018-04		
	Based on CS_STA_TEM-11_SAPtemplate_v01	M-11_SAPtemplate_v01		Page 7 I 16

Due to logistical reasons (2 hTEE devices available for the study) inclusion of a maximum of two patients into the groups applying hTEE was possible at the same time. Randomization and recruitment was therefore interrupted as soon as a second patient has been randomized into a treatment group in which hTEE was applied to preserve allocation concealment. Randomization and recruitment have been restarted as soon as at least one hTEE device has been available for further patients.

#### 4.4. Blinding

This is an open-label study, as the method used cannot be concealed from the physician. The patient is usually not in a condition to realize the treatment he is assigned to. The physician assessing stability of the patient is not blinded to the treatment of the patient, or to additional information available like conventional monitoring.

The trial statistician will not be blinded. Blinding of the statistician would not be feasible, because the trial is open-label and the database contains information on the study arm in several forms.

#### 5. Hypothesis

The primary study hypothesis is that hemodynamic monitoring using hTEE in critically ill patients with hemodynamic compromise allows for an expedited reversal of circulatory impairment compared to standard ICU monitoring. The secondary hypothesis is that more frequent monitoring results in shorter reversal of hemodynamic shock as compared to standard monitoring.

#### 6. Study endpoints

#### 6.1. Primary endpoints

The primary study outcome is the time from study inclusion to resolution of circulatory shock.

 Time to resolution of hemodynamic instability defined as systemic mean blood pressure (MAP) > 60mmHg for at least 4 hours after discontinuation vasopressors or inotropes (dobutamine, milrinone, norepinephrine or epinephrine). The criterion is considered fulfilled if >90% of MAP measurements (occurring every 1 - 2 minutes) is > 60mmHg for a 4 hour period.

#### 6.2. Secondary endpoints

• Time to death

CTU Bern	Statistical Analysis Plan ImaCorII	Date effective:	2018-04-24	
	Based on CS_STA_TEM-11_SAPtemplate_v01			Page 8 I 16

- Time to resolution of clinical signs of hypoperfusion as a composite of capillary refilling time < three seconds, urine output > 0.5 mL/kg/h for at least 4 hours, and blood lactate < 2 mmol/L.
- Use of conventional hemodynamic monitoring (3 binary endpoints):
  - o pulmonary artery catheter (yes/no),
  - o central venous catheter (yes/no),
  - conventional echocardiography (yes/no)
- Occurrence of adverse events assumed to be due to prolonged hemodynamic impairment and treatment with vasopressors/inotropes (as binary yes/no outcomes):
  - cardiac arrhythmias: non sustained ventricular tachycardia (≥ 4 beats), sustained ventricular tachycardia, ventricular fibrillation, atrial fibrillation, atrial flutter, other supraventricular tachycardia, new onset AV block (I/II/III), or asystole,
  - Excessive vasoconstriction: occurrence of acute myocardial infarction, skin necrosis, or secondary bowel or limb ischemia or stroke,
  - Secondary infections (catheter related infections, VAP, new onset of sepsis).

#### 6.3. Further outcomes of interest

Following outcomes will only be analysed descriptively:

- Length of time with need for organ support (mechanical ventilation, renal-replacement therapy)
- Length of stay (LOS) in the ICU
- LOS in hospital
- Death during ICU admission
- Death during hospital admission

#### 6.4. Safety endpoints (specific for use of hTEE only)

Occurrence of complications potentially attributed to the use of hTEE

- o Oral, pharyngeal, esophageal or gastrointestinal bleeding or injury
- Need for additional sedation and/or muscle relaxants for hTEE probe placement and hTEE assessment

#### 7. Data management

#### 7.1. Data export

Clinical study data are in a database format (REDCap) and will be imported into R by the trial statistician for data preparation, validation and analysis. The database system was set up by the investigators, and thus contains no data validation and error checks.

CTU Bern	Statistical Analysis Plan ImaCorll	Date effective: 20		
	Based on CS_STA_TEM-11_SAPtemplate_v01			Page 9 I 16

#### 7.2. Data validation

All variables used in the analysis, including the derived variables, will be checked for missing values, outliers, and inconsistencies and queried.

#### 7.3. Data preparation

The primary endpoint will be derived as the difference in hours between the date and time of randomization and the date and time of resolution of clinical shock. The competing risk of death for the primary outcome will be derived as the difference in hours between the date and time of randomization and the date and time of discontinuation of therapy before death.

Secondary and further endpoints will be derived as follows:

- Time to death (in hours) will be derived as the difference in hours from randomization to discontinuation of therapy before death.
- Time to resolution of clinical signs of shock will be derived as the difference in hours from randomisation to the latest time of any of the three: first lactate below 2 mmol/L, urine output above 0.5 ml/kg body weight or first capillary refilling time below three seconds
- Pulmonary artery catheter is yes if it was yes during any assessment
- Central venous catheter is yes if it was yes during any assessment
- Conventional echocardiography will be regarded as yes if TEE or TTE was used during any assessment
- Cardiac arrhythmias will be derived from any non sustained ventricular tachycardia (≥ 4 beats), sustained ventricular tachycardia, ventricular fibrillation, atrial fibrillation, atrial flutter, other supraventricular tachycardia, new onset AV block (I/II/III), or asystole
- myocardial infarction, skin necrosis, and stroke will be taken as is
- secondary bowel or limb ischemia will be derived from any bowel ischemia or any limb ischemia
- secondary infections will be derived from any catheter infection, VAP infection or sepsis
- Length of time with organ support (in hours) will be derived from length of time with mechanical ventilation and/or renal replacement therapy. If a patient received both, times will be added. If therapies are overlapping, time will only be counted once.
- Length of time in ICU (in hours) will be taken from eCRF as is.
- Length of time in hospital (in hours) will be taken from eCRF as is.

CTU Bern			2018-04-24
CTO Bern	Based on CS_STA_TEM-11_SAPtemplate_v01		Page 10 I 16

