#### **10.** Deviations from the protocol

Header	Change	Reason		
Primary objective	Removed the duration and amount of vasopressor use from the primary objective	Clarifies primary outcome		
Secondary endpoint	Time to death instead of death during ICU or hospital stay	Analyse as time to event outcome		
Secondary endpoint	Defined composites of adverse events as outcomes	Adverse events of interest were listed in the protocol, without defining composites		
Descriptive endpoints	Moved following outcomes from secondary endpoints Length of time with need for organ support (mechanical ventilation, renal-replacement therapy) Length of stay (LOS) in the ICU LOS in hospital Death during ICU admission Death during hospital admission	Only descriptive analysis of these outcomes is planned		
Statistical analysis	Use of a competing risk model for the primary outcome	To account for the competing risk of death		
Primary analysis	Defined the method of monitoring as primary comparison, and the frequency of monitoring as secondary comparison.	We do not have power to analyse the data as factorial.		

CTU Bern	Statistical Analysis Plan ImaCorII	Date effective:	2018-04-24
	Based on CS_STA_TEM-11_SAPtemplate_v01		Page 15 I 16

D UNIVERSITÄT BERN

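### SAP section 7.3 ends the time-to-death endpoint at discontinuation of therapy, while the patient is still alive, and section 10 does not declare it

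*SAP*

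**What the plan says.** Sections 2 and 6.2 of the SAP list time to death among the secondary outcomes without any qualifier. Section 9.5.1, under the secondary endpoints, keeps that name: "The secondary outcome time to death will be evaluated using Cox proportional-hazards regression". The model is adjusted for monitoring frequency.

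Section 7.3, which fixes how endpoints are computed, says: "Time to death (in hours) will be derived as the difference in hours from randomization to discontinuation of therapy before death". The competing event for the primary outcome gets the same end point, as the difference between "the date and time of randomization and the date and time of discontinuation of therapy before death".

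Section 10 lists departures from the protocol. Its entry for this endpoint reads "Time to death instead of death during ICU or hospital stay", and the reason given is only that the outcome is to be analysed as a time to event. The end date is not mentioned. Section 4.4 describes the setting: "This is an open-label study, as the method used cannot be concealed from the physician".

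**The concern.** A reader of the results will take time to death to end at death. Under section 7.3 it ends at an earlier clinical decision. The rule also looks ahead: discontinuation counts as an event only in patients who later die, so the event is placed at a time when the patient was alive, on the strength of what happened afterwards.

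For the resolution endpoints the date can be defended, since recovery is arguably no longer pursued once therapy stops. That argument does not turn discontinuation into death. In an open-label trial it also makes the event time of a mortality endpoint depend directly on a decision that may be taken with knowledge of the arm. If the lag from discontinuation to death, or the share of deaths preceded by discontinuation, differed between arms, the curves could separate early without any difference in when patients died.

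**Working it through.** No figure in the SAP is at issue, so there is none to reproduce. The check has two parts.

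**1. The sections side by side.** Let a patient be randomised at time 0, have therapy discontinued at time d and die at time t, with d < t.

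- Sections 2, 6.2 and 9.5.1: event time t, as the name implies.
- Section 7.3: event time d, too early by the lag t − d.
- A second patient whose therapy is also discontinued at d but who survives has no event at d. The two differ only in what happened after d.
- Death status is the same under both rules; only the event time moves. With a fixed horizon, a death just beyond it can be pulled inside. For the primary outcome, cut at 6 days, a patient whose therapy stops before day 6 and who dies after it counts as a competing event within the window.

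**2. How much it could matter.** The SAP gives neither mortality, nor the share of deaths preceded by discontinuation, nor the lag. All inputs here are assumptions: 30% die in both arms, at identical exponential times with a median of 96 h among those who die (mean 96/ln 2 = 138.5 h). Discontinuation precedes 80% of deaths in one arm and 30% in the other, with an exponential lag of mean L.

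The share of eventual deaths still to come at H hours is S(H) = 0.5^(H/96). With a share p of deaths re-dated, the apparent mortality by H is

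0.30 × {1 − S(H) × [1 − p + p/(1 + L/138.5)]}.

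Example, H = 72 and L = 48: S = 0.5^0.75 = 0.5946 and 1/(1 + 48/138.5) = 0.743.

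- True, both arms: 0.30 × (1 − 0.5946) = 12.2%.
- p = 0.8: bracket 0.2 + 0.8 × 0.743 = 0.794; 0.30 × (1 − 0.5946 × 0.794) = 15.8%.
- p = 0.3: bracket 0.7 + 0.3 × 0.743 = 0.923; 0.30 × (1 − 0.5946 × 0.923) = 13.5%.

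The Cox columns come from large simulations of the same scenario, where the true hazard ratio is 1.

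| Horizon | True mortality, both arms | Re-dated, L = 24 h (80% v 30% arm) | Re-dated, L = 48 h (80% v 30% arm) | Shift in Cox HR, L = 24 h | Shift in Cox HR, L = 48 h |
|---|---|---|---|---|---|
| 72 h | 12.2% | 14.3% v 13.0% | 15.8% v 13.5% | about 0.13 | about 0.20 |
| 6 days | 19.4% | 20.6% v 19.9% | 21.6% v 20.2% | about 0.06 | about 0.10 |
| 28 days | 29.8% | 29.8% v 29.8% | 29.8% v 29.8% | 0.03 or less | 0.03 or less |

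With L = 6 h the shift is 0.04 or less at every horizon.

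At trial size (250 v 250) the 28-day shift in the log hazard ratio was 0.004, 0.012 and 0.020 for mean lags of 6, 24 and 48 h. The standard error is about 0.16 (500 × 0.30 = 150 deaths; 2/√150 = 0.16). The most unfavourable cell, 48 h lag at 72 h, shifted 0.17 against a standard error of 0.24. Rejection at the 5% level stayed between 3% and 9% across scenarios.

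A different null scenario used 500 patients, 25% mortality at 28 days with constant hazard, 50% to 90% of deaths re-dated, and mean lags of 2 to 48 h, equal or unequal between arms. It gave hazard ratios of 1.00 to 1.02 and rejection of 4% to 6%.

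**The case against.** The strongest defence is that section 7.3 is the place where the SAP defines its endpoints operationally, that it states the rule openly, and that it uses the same date as the competing event. Section 6.2 gives only a name. On that view this is a disclosed choice with a poor label. It is fair that nothing is hidden, but the label is what will be reported, and neither section 10 nor any planned sensitivity analysis covers the difference.

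A reader might infer more than the SAP supports.

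- **That the mortality result would mainly describe withdrawal practice.** The contrast of 80% v 30% and the lags of 24 to 48 h are invented for illustration. Section 4.4 says "The physician assessing stability of the patient is not blinded to the treatment of the patient", but does not say who decides to discontinue therapy. That the arm influences the decision is an inference from the open-label design.
- **That the 72 h or 6-day figures apply.** The SAP sets no such cut for time to death. Section 9.5.1 says "The primary outcome will be censored after 6 days in the primary analysis", and the 3- and 28-day analyses in section 9.6 also concern the primary endpoint. The short-horizon rows show sensitivity, not a planned analysis.
- **That the actual time of death is free of the decision.** Discontinuing therapy may itself change when the patient dies. Using the time of death removes the artificial lag, not every effect of an unblinded decision.

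Death during ICU and hospital admission is still reported descriptively (section 6.3), which gives a check that does not depend on dating. All of this limits the consequence; the mismatch itself stands.

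**Conclusion.** The point holds as a mismatch between the endpoint's name and its derivation. Followed as written, section 7.3 gives event times that are too early in every patient whose therapy was discontinued before death, under a mortality label, and section 10 does not declare it.

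The likely numerical effect on the Cox result is small over long follow-up: about 0.03 or less on the hazard ratio at 28 days under the assumed inputs, well inside sampling error. It becomes noticeable only if follow-up is short, the lag is long, and the lag or the share of deaths preceded by discontinuation differs between arms. The SAP contains no figures from which to judge whether that is so. The term therapy is also undefined in section 7.3, so the number of deaths affected is unknown.

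The point does not challenge who is counted as having died, nor the use of discontinuation as the competing-event date for the resolution endpoints. It should be corrected because the derivation is wrong for the stated endpoint and the correction is simple, not because a large bias has been shown.

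**What to change.** - In section 7.3, derive time to death from randomisation to the recorded date and time of death.
- Keep discontinuation of therapy only as the date of the competing event in the resolution endpoints, and give that event an accurate name, such as discontinuation of therapy followed by death.
- Tabulate by arm the number of deaths preceded by discontinuation and the lag from discontinuation to death.
- If the time of death was not recorded, use the date of death; otherwise rename the endpoint for what it measures and declare the change in section 10.

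The cost is a few lines of SAP text, one derivation and one short table; no model changes. Death in ICU and in hospital are already outcomes, so a date of death is probably held, but the SAP does not confirm that the hour was captured. That should be checked in the database first.
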